3. STUDY DESIGN

3.1. General Study Design and Study Schematic Diagram

This is a 24-week treatment, multicenter, open-label, randomized, parallel group comparison feasibility study of SoC treatment versus using the eMDPI DS, including inhaler, App, DHP (Cloud solution), and dashboard, to optimize outcomes in patients at least 13 years of age or older with asthma.

The study will consist of a screening/baseline visit (Visit 1), a 24-week, open-label treatment period with Visit 2 (either in-person or remote) at Week 12 and Visit 3 at Week 24, and a follow-up telephone call (2 weeks following treatment completion).

Patients with suboptimal asthma control will be enrolled in the study and randomized, in a 4:3 ratio, respectively, to 1 of 2 parallel groups (Table 4), stratified by investigational center.

Table 4: Description of Treatment Groups

DS group	SoC group
FS eMDPI ^a + App	Current ICS/LABA and any additional controller medication for asthma (except for biologics)
Albuterol eMDPI + App	Current rescue medication
DHP (Cloud solution)	Not applicable
Provider-facing dashboard	Not applicable

^a iHCP can add another controller medication other than an ICS with LABA, including a biologic, to the DS patient's treatment, if needed.

Albuterol eMDPI=Albuterol electronic multidose dry powder inhaler; App=smart device application; DHP=Digital Health Platform; DS=Digital System; FS eMDPI=fluticasone propionate/salmeterol electronic multidose dry powder inhaler; ICS=inhaled corticosteroid; iHCP=investigational center health care provider; LABA=long-acting beta₂ agonist.

The DS group patients will use the FS eMDPI and the Albuterol eMDPI with a common App, DHP (Cloud solution), and dashboard. The SoC group patients, who will include eligible patients treated with their current treatment provided by the investigational center to the patient, based on asthma guidelines, will not use the DS during the treatment period. Similar data will be collected regarding outcomes for both groups: ACT after 24 weeks, BMQ, BIPQ, Mini-AQLQ, and WPAI questionnaire responses, and the frequency of CAEs.

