The SoC group will be followed according to the clinical judgment of the investigator; the asthma of patients in the SoC group will be managed in a manner consistent with the clinical judgement of the investigator and based on asthma management guidelines (eg, GINA). Similar to the management of the SoC group, the DS group patients will be followed by the investigational centers with the addition of objective information on FS eMDPI and Albuterol eMDPI usage being available to both patients and investigational centers through the App and the dashboard, respectively. The iHCPs will check the dashboard at least once a week and use this information, along with any other additional information about the patient, as per their clinical judgement, to modify patients' asthma management. The investigator may, if indicated, modify the patient's regime, including adding asthma controllers or biologics as otherwise clinically indicated in the judgement of the investigator. Clinically Driven Assessments for both groups, if necessary, should be arranged, per the clinical judgement of the iHCP managing the patient, and can be via a telephone call or an on-site visit.

For all patients, at Visit 2, Visit 3, and any Clinically Driven Assessments, if necessary, the iHCP will record answers to Asthma Management questions, including discussions regarding adherence, or inhaler technique, treatment adjustments, or additions of new treatments, including biologic medication usage. Additionally, in the case of a Clinically Driven Assessment (for patients in the DS group), the iHCP will be asked whether or not the contact with the patient was originated from the iHCP interaction with the dashboard.

Visit 2 (if it is an in-person visit) will include dispensing of new inhalers to the DS group patients and return of used or unused inhalers that were dispensed to the patients previously. New FS eMDPI devices will continue to be shipped directly to patients periodically after Visit 2 until the end of treatment. The ACT will be completed and scores registered.

At the end of the treatment period (24 weeks), final assessments of the DS and SoC groups will be completed, as specified in Table 5, and the rest of the inhalers that were dispensed to the DS group patients will be returned. A follow-up telephone call will be made by the investigational

center to all patients, 2 weeks later, and will confirm that the DS group patients have returned to their previous asthma treatments.

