3.5. Schedule of Study Procedures and Assessments

Study procedures and assessments with their time points are presented in Table 5. Detailed descriptions of each method of procedures and assessments are provided in Section 6 (efficacy assessments) and Section 7 (safety assessments). Study procedures and assessments by visit are listed in Appendix B.

Table 5: Study Procedures and Assessments

Study period	Screening/ Baseline visit	Treatment period (24 weeks)					Follow- up telephone call ^a	Clinically driven assessment(s) (if necessary)			
									End of treatment/ ET visit		
Visit number	Visit 1	DTP	DTP	DTP	Visit 2 ^b		DTP	DTP	Visit 3		
Treatment week		W3	W6	W9	W12	W15	W18	W21	W24	W26	
Day and allowed time windows	Day 1 ^c				84 days ±3 days				168 days +3 days	182 +7 days	
Procedures and assessments											
Informed consent/assent	X										
Inclusion and exclusion criteria	X										
Medical history	X										
Current medication and treatment history related to asthma	X										
Inform patients of study restrictions and compliance requirements	X										
ACT ^d	X				Xe				X		
Mini-AQLQ and WPAI ^d	X								X		
BMQ-S11 and BIPQ ^d	X								X		
Assign patient number and provide unique email account for DS group patients	X										
Train DS group in use of test IMP	X										
Dispense test IMP to DS group											
FS eMDPI ^f	X	X	X	X	X	X	X	X			X
Albuterol eMDPI ^g	X				X						
Dose confirmation of test IMP in IRT ^h	X	X	X	X	X	X	X	X			X ⁱ
Registration and onboarding (App)	X										

Version 2.0

CLN0035849

Page 41 of 98

Approved

Study period	Screening/ Baseline visit	Treatment period (24 weeks)						Follow- up telephone call ^a	Clinically driven assessment(s) (if necessary)		
									End of treatment/ ET visit		
Visit number	Visit 1	DTP	DTP	DTP	Visit 2 ^b	DTP	DTP	DTP	Visit 3		
Treatment week		W3	W6	W9	W12	W15	W18	W21	W24	W26	
Day and allowed time windows	Day 1 ^c				84 days ±3 days				168 days +3 days	182 +7 days	
Procedures and assessments											
Adverse events and adverse device effects inquiry	X				X				X	X	X
iHCP will ask Asthma Management questions regarding adherence, inhaler technique, treatment adjustments, and biologic medication usage					X				X		X
Vital signs measurement	X								X		
Concomitant medication inquiry	X				X				X		X
Administer post- intervention PRO (SUS) to DS group patients ^j									X		
Administer SUS to iHCPs									X		
Test IMP collection and accountability					X				X		

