7. ASSESSMENT OF SAFETY

In this study, safety will be assessed by qualified study personnel by evaluating reported adverse events, adverse device effects, vital signs measurements, and use of concomitant medications.

Adverse events are categorized by ICH guidelines, and adverse device effects are categorized and classified according to International Organization for Standardization (ISO) standard 14155:2011(E).

Device deficiencies that are not associated with an adverse event as well as those that have the potential to cause a serious adverse event are covered in Appendix F.

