7.1. Adverse Events

7.1.1. Definition of an Adverse Event

An adverse event is any untoward medical occurrence, unintended disease or injury, or untoward clinical signs (including abnormal laboratory findings) in patients or clinical investigation subjects, users or other persons, whether or not related (causal relationship) to the pharmaceutical product (treatment), investigational medical device, or comparator. This definition includes events related to the procedures involved. For users or other persons, this definition is restricted to events related to investigational medical devices.

An adverse event can, therefore, be any unfavorable and unintended physical sign, symptom, or laboratory parameter that develops or worsens in severity during the course of this study, or significant worsening of the disease under study or of any concurrent disease. A new condition or the worsening of a pre-existing condition will be considered an adverse event. Stable chronic conditions (such as arthritis) that are present before study entry and do not worsen during this study will not be considered adverse events.

Accordingly, an adverse event can include any of the following:

- intercurrent illnesses
- physical injuries
- events possibly related to concomitant medication
- significant worsening (change in nature, severity, or frequency) of the disease under study or other pre-existing conditions
- drug/drug, drug/device, or device/device interactions
- events occurring during diagnostic procedures of this study

Worsening of asthma that occurs during the study that is not typical of the patient's daily symptoms or leads to the patient's discontinuation will be considered an adverse event.

A CAE will be defined by 1 of the following: 1) in-patient hospitalization because of asthma, 2) emergency treatment because of asthma, 3) a worsening of asthma symptoms leading to the use of prednisone or systemic corticosteroids for 3 days or more, or 4) a reduction in forced

57

expiratory volume in 1 second (FEV₁) of 20% or greater. Patients will be instructed to contact the study investigational center in the event of a CAE.

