The date and reason for the Clinically Driven Assessment (eg, treatment step up, treatment step down, adherence discussion, treatment for an asthma exacerbation, or other clinical encounters generated by the data from the FS eMDPI or Albuterol eMDPI), as well as any other data obtained from procedures and assessments, will be recorded in the patient's source documents and the case report form (CRF) for patients in both groups, during the 24-week treatment period.

The following procedures and assessments will be performed at a Clinically Driven Assessment:

- conduct adverse events and adverse device effects inquiry
- conduct concomitant medication inquiry
- dispense FS eMDPI or Albuterol eMDPI, as needed (if on-site and necessary). If the patient's dose is being changed at this visit, it will be necessary to access the IRT system to confirm the dose of test IMP for the next DTP shipment.
- iHCP asks Asthma Management questions

Other procedures and assessments may be performed at the discretion of the investigator.

5. Procedures for Follow-up Telephone Call (Day 182 + 7 days)

The following procedures and assessments will be performed at the follow-up telephone call:

- conduct adverse events and adverse device effects inquiry
- for DS group patients, confirm that the patient has returned to previous asthma treatment

85

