8.4. Adverse Events

All adverse events will be coded using the MedDRA. Adverse events occurring on or after the treatment start date will be included in the summary tables while all of the adverse events will be listed in data listings.

A summary will be presented for adverse events in the following categories: all adverse events, adverse events determined by the investigator to be related to study drug, severe adverse events, serious adverse events, adverse events leading to withdrawal from the study, non-serious adverse events, device-related adverse events (DS group only), asthma related adverse events, and CAE related adverse events. The incidence of patients with an adverse event in each category will be summarized using descriptive statistics.

Summaries will be presented for all adverse events (overall and by severity), adverse events determined by the investigator to be related to study drug (overall and by severity), serious adverse events, adverse events leading to withdrawal from the study, non-serious adverse events, and device-related adverse events (DS group only).

The incidence of adverse events will be summarized using descriptive statistics by SOC and preferred term (all AEs overall will also be presented by just preferred term category). Patients are counted only once in each SOC category, and only once in each preferred term category. For the summaries by severity, patients are counted at the greatest severity. Adverse events with the missing flag indicating serious will be excluded from the summary of serious adverse events but included in the summary of non-serious adverse events.

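### The clinical asthma exacerbation (CAE) definition accepts a 20% FEV₁ fall on its own, but no FEV₁ is scheduled and no reference value is given, so by-arm CAE counts may partly reflect who was tested

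*Protocol*

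**What the plan says.** Protocol 7.1.1 treats the four criteria as alternatives: "A CAE will be defined by 1 of the following: 1) in-patient hospitalization because of asthma", then emergency treatment, then a systemic corticosteroid course of at least 3 days for worsening symptoms, and fourth a reduction in forced "expiratory volume in 1 second (FEV₁) of 20% or greater". It names no comparator for the reduction. It asks patients to contact the center when a CAE occurs, and it requires a CAE page in the CRF and source documentation for every event.

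Protocol 3.5 states: "Study procedures and assessments with their time points are presented in Table 5". That table has no spirometry row, and the visit lists in Appendix B have no such item. Section 7 assesses safety "by evaluating reported adverse events, adverse device effects, vital signs measurements, and use of concomitant medications". The one visible opening for lung function testing is in Appendix B, under Clinically Driven Assessments: "Other procedures and assessments may be performed at the discretion of the investigator".

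Protocol 3.1 lists, among the data collected in both groups, "questionnaire responses, and the frequency of CAEs". SAP 8.4 includes in its adverse event summary "asthma related adverse events, and CAE related adverse events", and SAP 8.1 has safety summaries presented by treatment group. For DS patients only, Protocol 3.1 adds: "The iHCPs will check the dashboard at least once a week and use this information".

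**The concern.** An outcome criterion that is sufficient on its own should be assessable in every patient, or at least with equal opportunity in each arm. This one is not assessable in a patient who receives exactly the scheduled procedures. Whether it is met depends on an investigator choosing to do spirometry and having some earlier value to compare with. Two centers could classify the same patient differently.

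The choice to test is made in an open-label trial in which one arm has an additional prompt for contact. If testing frequency differs between arms, the CAE frequency will differ even when the disease does not. The SAP's visible text neither separates the criteria nor counts the patients who had any FEV₁ measured, so a reader of the table could not tell the two explanations apart.

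**Working it through.** The documents give no figure to reproduce. The check sets the definition against the schedule and then illustrates the possible size.

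**Definition against schedule**

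1. Sufficiency. One of the four criteria is enough (Protocol 7.1.1), so an FEV₁ fall with no hospital stay, emergency treatment or corticosteroid course counts as a CAE.
2. Measurement. No FEV₁ appears in Table 5, in Appendix B for Visits 1 to 3, early termination, Clinically Driven Assessments or the follow-up call, or in Protocol Sections 6 and 7 as an assessment. Vital signs (Protocol 7.7) are blood pressure, pulse and respiratory rate. Apart from the abbreviation list, Protocol 7.1.1 is the only place where FEV₁ is mentioned. The inhalers do not fill the gap: they record inhalation parameters such as peak inhalation flow (SAP 8.3), not expired volume.
3. Comparator. No study baseline FEV₁ is scheduled, and the definition names none, so any comparison uses a value from outside the study.
4. Route to testing. The discretionary clause applies to Clinically Driven Assessments. Both arms can have these, by telephone or on site. In the DS arm, a contact prompted by the dashboard is also recorded as one (Appendix B, item 4).

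**Illustration of size**

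Let *b* be the share of patients with a CAE by criteria 1 to 3, *h* the share with a 20% fall and no other criterion, and *t* the share tested. With *b* and *h* equal in both arms and testing unrelated to *h*:

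- observed CAE share in an arm = *b* + *h* × *t*
- difference, DS minus SoC = *h* × (*t*DS − *t*SoC)

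All of *b*, *h* and *t* are assumptions. The denominators used below, 200 DS and 150 SoC, are the planned evaluable numbers (Protocol 9.1).

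| *b* | *h* | *t* SoC | *t* DS | SoC | DS | Difference (points) | Ratio |
|---|---|---|---|---|---|---|---|
| 20% | 5% | 10% | 20% | 20.5% | 21.0% | +0.5 | 1.02 |
| 10% | 5% | 10% | 50% | 10.5% | 12.5% | +2.0 | 1.19 |
| 10% | 10% | 10% | 50% | 11.0% | 15.0% | +4.0 | 1.36 |
| 10% | 10% | 10% | 10% | 11.0% | 11.0% | 0 | 1.00 |
| 10% | 5% | 30% | 10% | 11.5% | 10.5% | −1.0 | 0.91 |
| 10% | 10% | 30% | 10% | 13.0% | 11.0% | −2.0 | 0.85 |

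In the third row, SoC is 0.10 + 0.10 × 0.10 = 0.110 (16.5 of 150) and DS is 0.10 + 0.10 × 0.50 = 0.150 (30 of 200). True disease is identical in every row. The sign follows the testing imbalance, and the size scales with *h*.

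**The case against.** The strongest reply is that little visible weight rests on CAE. It is not the primary endpoint and does not define any of the seven named secondary endpoints. Protocol 3.1 says that its frequency will be collected in both groups and specifies no test, and the visible SAP makes it one category in a descriptive safety table. Counting events as they emerge in ordinary care also fits a trial that dictates no clinical decisions. All of this stands, and it is why the point is minor. It does not explain how a reader should interpret a by-arm count that contains an unscheduled criterion.

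The second reply is that the direction is unknown. Clinically Driven Assessments exist in both arms and may be by telephone, where spirometry would not be expected. Investigators who lack device data on SoC patients might test them more. This also stands. A reader might infer that the count is biased against DS. The documents show an extra prompt for contact in DS but give no testing rates, so they do not support a direction.

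The third reply is that criterion 3 is also a clinician's decision in the same open-label setting, so dropping criterion 4 does not remove all dependence on contact. That is fair. Even so, criteria 1 to 3 are care events that the scheduled adverse event and medication inquiries at Visits 2 and 3 can pick up in every patient who attends. An FEV₁ fall has no such inquiry.

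Finally, parts of both documents are blacked out, including the body of SAP 6.4. CAE may be used or defined further there. The mismatch between the visible definition and the visible schedule remains.

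**Conclusion.** The definition and the schedule do not match. A CAE can rest on an FEV₁ fall alone, yet no FEV₁ is scheduled and no reference value is stated. The by-arm CAE frequency may therefore partly reflect testing. The documents fix neither sign nor size; the range of −2.0 to +4.0 points rests wholly on the assumed inputs. Larger figures are easy to produce. With 30% of tested patients qualifying on FEV₁ alone, and 35% of DS against 5% of SoC patients tested, the difference is 0.30 × (0.35 − 0.05) = 9 points. That would require 0.30 × 0.35 = 10.5% of DS patients, 21 of 200, to be FEV₁-only events, and nothing in the documents supports it.

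Two other stronger readings go too far. A reader might infer that FEV₁ is never measured; the supportable statement is that it is never scheduled, since discretionary testing is allowed and earlier clinic values may exist. A reader might also infer that the main results are compromised; the ACT responder analysis, the sample size and the named secondary analyses do not depend on the CAE definition. Severity is minor.

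**What to change.** In SAP 8.4, and in any other section that summarises CAEs:

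- tabulate CAEs by qualifying criterion and arm;
- base the by-arm CAE frequency on criteria 1 to 3;
- report FEV₁-only events separately by arm, with the number of patients in each arm who had any FEV₁ measured.

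All such events stay as adverse events and on the CAE page, so no safety information is lost. No procedure is added and patient care is unchanged.

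The cost is a few sentences and one extra table block, which can be added while the SAP can still be amended before database lock (SAP 2.5.2). If the CAE page does not already record the qualifying criterion and whether FEV₁ was measured, those items would have to be taken from source documents. The downsides are that the headline count excludes FEV₁-only events, and that criterion 3 may still respond somewhat to contact frequency, which a footnote should state.

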7.1.2. Recording and Reporting of Adverse Events

For recording of an adverse event, the study period is defined for each patient as the time period from signature of the ICF to the end of the follow-up period (end of study [follow-up telephone call]). The period for reporting treatment-emergent adverse events is defined as the period after the first dose of IMP is administered and until the end of the follow-up period.

All adverse events that occur during the defined study period must be recorded both on the source documentation and the CRF, regardless of the severity of the event or judged relationship to the IMP. For serious adverse events, the serious adverse event form must be completed, and the serious adverse event must be reported immediately (Section 7.1.5.3.1). The investigator does not need to actively monitor patients for adverse events after the defined period.

At each contact with the patient, the investigator or designee must question the patient about adverse events by asking an open-ended question such as "Have you had any unusual symptoms or medical problems since the last visit? If yes, please describe." All reported or observed signs and symptoms will be recorded individually, except when considered manifestations of a medical condition or disease state. A precise diagnosis will be recorded whenever possible. When such a diagnosis is made, all related signs, symptoms, and any test findings will be recorded collectively as a single diagnosis on the CRF and, if it is a serious adverse event, on the serious adverse event form.

The clinical course of each adverse event will be monitored at suitable intervals until resolved, stabilized, or returned to baseline; or until the patient is referred for continued care to a healthcare professional; or until a determination of a cause unrelated to the IMP or study procedure is made.

The onset and end dates, duration (in case of adverse event duration of less than 24 hours), action taken regarding IMP, treatment administered, and outcome for each adverse event must be recorded both on the source documentation and the CRF.

The relationship of each adverse event to IMP and study procedures, and the severity and seriousness of each adverse event, as judged by the investigator, must be recorded as described below.

Further details are given in the Safety Monitoring Plan.

7.1.3. Severity of an Adverse Event

The severity of each adverse event must be recorded as 1 of the following:

Mild: No limitation of usual activities

Moderate: Some limitation of usual activities **Severe:** Inability to carry out usual activities

